3. STUDY OBJECTIVES

3.1. PRIMARY OBJECTIVE

The primary objective of this study is to evaluate the treatment effect of NGM282 on absolute liver fat content as measured by magnetic resonance imaging protein density fat fraction (MRI-PDFF) in subjects with histologically confirmed Nonalcoholic Steatohepatitis (NASH).

3.2. SECONDARY OBJECTIVE(S)

- Assess the safety and tolerability of NGM282 in subjects with NASH with up to 24 weeks of treatment with NGM282.
- Evaluate the percent change from Baseline in absolute liver fat content at Weeks 6, 12, 24, 30 (End of Treatment, EOT).
- Evaluate the percentage of normalization for liver fat content at EOT.
- Evaluate the liver fat content response rate as defined by
 - a \geq 5(%) decrease in absolute liver fat content
 - a \geq 30% relative decrease in absolute liver fat content
- Evaluate the actual and percent changes from Baseline to EOT as well as the percentage of normalization of the following parameters: alanine aminotransferase (ALT), aspartate aminotransferase (AST), triglycerides, bilirubin (total and direct), and gamma-glutamyl transferase (GGT). The percentage of normalization will be assessed for ALT and triglycerides. Percentage of normalization will also be investigated for a clinically meaningful threshold for triglycerides.
- Evaluate the actual and percent changes from Baseline to EOT for the following (if collected as part of the cohort):
 - Total cholesterol, high-density lipoproteins-cholesterol (HDL-C), low-density lipoproteins-cholesterol (LDL-C), triglycerides, and lipoprotein particles
 - [REDACTED]
 - Fasting blood glucose, insulin levels, [REDACTED], and homeostasis model assessment-estimated insulin resistance (HOMA-IR)
 - PRO-C3 and Enhanced Liver Fibrosis (ELF) Score
 - Body weight, body mass index (BMI), and waist circumference
 - 7-alpha-hydroxy-4-cholest-3-one (C4) and serum bile acids

Amendment Final V 2.0

- Bile-mediated absorption as measured by vitamin D, International Normalized Ratio (INR), and fecal fat content
- Evaluate liver histologic response
 - Improvement in liver fibrosis by ≥ 1 stage by NASH Clinical Research Network (CRN) criteria with no worsening of steatohepatitis
 - Resolution of NASH (defined as an NAS score of 0 or 1 for inflammation and 0 for ballooning) with no worsening of fibrosis as determined by the NASH CRN criteria
- Evaluate the efficacy and safety of rosuvastatin administered in response to increases in total cholesterol and LDL-C from NGM282 treatment.

3.3. EXPLORATORY OBJECTIVE(S)

- [REDACTED]
- [REDACTED]
- [REDACTED]
- [REDACTED]
- [REDACTED]
- [REDACTED]

3.4. STUDY DESIGN

Protocol 15-0105 is comprised of a double-blind placebo controlled parallel group study followed by additional open-label single blind and placebo-controlled 24-week histology cohorts studies. This analysis plan covers the placebo-controlled 24-week histology cohorts study designed to assess the efficacy and safety of NGM282. All subjects in the placebo-controlled 24-week histology cohort will be treated with NGM282 for 24 weeks once daily and will be followed for 6 weeks after completing final study-drug dose. No dose reductions will be allowed in this placebo-controlled 24-week histology cohort.

In the placebo-controlled 24-week histology cohort, approximately up to 75 subjects (50 NGM282 and 25 placebo) will be enrolled from ~10 U.S. sites and treated for 24 weeks with a 6-week safety follow-up. Subjects will be required to meet enrollment criteria similar to those of the open-label single-blind cohort as specifically defined in protocol Section 8.1.1 with the exception of the following: 1) only subjects with Stages 2 and 3 fibrosis at Screening will be enrolled. At Day 1 eligible subjects will be randomized into the study and stratified as either fibrosis stage 2 or 3.

Amendment Final V 2.0

The dose of NGM282 to be studied will be 1 mg [REDACTED]

[REDACTED] The active dose selection for this cohort will be blinded to the study site and subjects throughout the study period.

The first dose of NGM282 or placebo (Day 1) and doses at Weeks 2, 4, 6, 8, 12, 18, and 24 study visits will be self-administered in the clinic, with all other doses throughout the treatment period self-administered at home. Self-administration of NGM282 should occur as close as possible to the same time each day for every dose. Subjects will return to the clinic on Weeks 2, 4, 6, 8, 12, 18 and 24 for on-treatment assessments and to be dispensed NGM282 or placebo study-drug kits through Week 18. LDL-C will be evaluated at Weeks 2, 4, 8, and 12 in all subjects for possible increases in lipid levels associated with NGM282 administration.

Rosuvastatin will be started in subjects meeting specific LDL-C level criteria. The specific dosing and administration of Rosuvastatin will be based on whether the subject is statin naïve versus statin experienced and LDL-C levels at Weeks 2, 4, and 8 (LDL-direct may be used if LDL-C was not able to be analyzed). A decision about possible second-line lipid-lowering therapy with ezetimibe will be made on a case-by-case basis for subjects that have not achieved an adequate response or are unable to tolerate rosuvastatin. Bottles of Rosuvastatin tablets will be dispensed to all subjects initially and instructions to initiate dosing are dependent on observed lipid levels according to the dosing algorithm in (Appendix A). Week 24 will be the EOT clinic visit and subjects will return to the clinic at Week 30 (or 6 weeks after last dose of NGM282 or placebo) for an EOS follow-up visit. Subjects are required to undergo MRI performed during Screening and at Weeks 6, 12, 24 (EOT)/Early Withdrawal, and 30 (EOS) visits.

This cohort will have two other assessments performed to assess liver histology in addition to MRI-PDFF. [REDACTED]

[REDACTED] where available at the local radiology center.

3.5. DETERMINATION OF SAMPLE SIZE

[REDACTED]

Amendment Final V 2.0

[REDACTED] the assumptions of calculated sample-size estimates for 24-week efficacy used an NGM282 response of 50% versus 15% for placebo utilizing 80% power and alpha=0.05 with a 2:1 randomization scheme. Assuming a 15% drop-out rate, the planned sample size of 50 NGM282-treated subjects and 25 placebo subjects is sufficient to evaluate efficacy and support powering estimates for late-stage clinical trials.

4. ENDPOINTS

4.1. PRIMARY EFFICACY ENDPOINT

- The primary efficacy endpoint for this study will be the actual change in liver fat content as measured by MRI PDFF in subjects with histologically confirmed NASH after 24 weeks of treatment.

4.2. SECONDARY EFFICACY ENDPOINTS

- The actual and percentage change from Baseline in liver fat content by MRI-PDFF at Weeks 6, 12, 24, and 30.
- The percentage of normalization in liver fat content at EOT.
- The percentage of responders
 - a liver fat content decrease $\geq 5\%$
 - a liver fat content relative decrease by $\geq 30\%$
- The actual and percentage changes from Baseline to EOT as well as the percentage of normalization of AST, ALT, bilirubin (total, direct), triglycerides and GGT. Percentage of normalization by Week 24 will be investigated for these parameters (including clinically meaningful normalization of Triglycerides)
- The actual and percentage changes from Baseline to EOT of the following parameters: Total cholesterol, HDL-cholesterol, LDL-cholesterol, and lipoprotein particles.
- The actual and percentage changes from Baseline to EOT of the following parameters: [REDACTED], Pro-C3, ELF Score, Fasting blood glucose, insulin levels, HbA1c, [REDACTED], and HOMA-IR, Body weight, BMI, and waist circumference, C4 and serum bile acids, Bile-mediated absorption as measured by fat-soluble vitamins and fecal fat content.
- The percentage of liver histologic responders
 - Improvement in liver fibrosis by ≥ 1 stage by NASH Clinical Research Network (CRN) criteria with no worsening of steatohepatitis
 - Resolution of NASH (defined as an NAS score of 0 or 1 for inflammation and 0 for ballooning) with no worsening of fibrosis as determined by the NASH CRN criteria.

4.3. EXPLORATORY ENDPOINTS

- [REDACTED]

Amendment Final V 2.0

- [REDACTED]
- [REDACTED]
- [REDACTED]
- [REDACTED]
- [REDACTED]

4.4. SAFETY ENDPOINTS

The safety and tolerability endpoints will consist of incidence of adverse events (AEs) and local injection site reactions, as well as changes in clinical laboratory tests (hematology, biochemistry and urinalysis), vital signs, electrocardiogram (ECG) and physical examinations.

Amendment Final V 2.0

5. ANALYSIS POPULATIONS

5.1. INTENT-TO-TREAT POPULATION

All randomized subjects will be included in the Intent-to-Treat (ITT) population. The ITT population will be used to summarize subject enrollment and disposition and will be based on randomized treatment if this differs from actual treatment received.

5.2. SAFETY POPULATION

The Safety Population will include all enrolled subjects who receive at least one dose of NGM282 (full or partial) and have at least one post-dose safety evaluation.

All safety endpoints will be summarized using the Safety population and will be based on actual treatment received if this differs from the enrolled treatment.

5.3. EFFICACY POPULATION

The Efficacy Population will include all enrolled subjects who receive at least one dose (full or partial) of NGM282 and have at least one valid, non-missing post-dose efficacy/PD parameter value.

All efficacy and PD endpoints will be summarized and analyzed using the Efficacy population. This will be the main population for the analysis of efficacy and PD endpoints. The Efficacy population will be based on enrolled treatment if this differs from actual treatment received.

5.4. PER PROTOCOL (PP) POPULATION

[REDACTED]

5.5. LIVER HISTOLOGY POPULATION

[REDACTED]

5.6. PROTOCOL DEVIATIONS

Subject data will be examined prior to database lock for evidence of protocol deviations in order to identify subjects with major protocol violations which would exclude such subjects from the Per Protocol Population. Possible protocol deviations will be independently reviewed and approved by NGM Biopharmaceuticals Australia Pty Ltd. All protocol deviations will be detailed in a listing by subject and treatment group for the ITT Population. Deviations will be categorized as minor or major based of predefined criteria and assigned by the study team prior to database lock.

Protocol deviations are defined as follows:

- Not meeting all inclusion and exclusion criteria, as detailed in Sections 3.5 of the SAP
- Intake of any prohibited medications, as detailed in Section 6.5 of the protocol
- Failure to follow the conduct of the study

6. GENERAL ASPECTS FOR STATISTICAL ANALYSIS

6.1. GENERAL METHODS

Unless otherwise specified, for numeric data, descriptive statistics will include the number of subjects with data to be summarized (n), mean, standard deviation (SD), median, minimum (min), and maximum (max). The same number of decimal places as used in the raw data will be presented when reporting min and max, 1 decimal place more than in the raw data will be presented when reporting mean and median, and SD. If the raw data have 3 decimals or more, 3 decimals will be presented for the mean, median, min and max, and SD.

All categorical/qualitative data will be presented using frequency counts and percentages. All percentages will be rounded to 1 decimal point, with the denominator being the number of subjects in the relevant population, unless otherwise stated. Percentages equal to 100 will be presented as 100%; percentages will not be presented for zero frequencies but the categories whose counts are zero will be displayed for the sake of completeness.

Unless otherwise specified, all the tables will be summarized by treatment group (and overall, if applicable). All the listings will be sorted by treatment group, subject number and assessment date/time.

All confidence intervals (CIs) will be two-sided and will use 95% confidence levels. Any analyses requiring significance testing will use a two-sided test at the 5% significance level, unless otherwise specified.

In general, only data from nominal scheduled visits will be presented in the summary tables and figures unless otherwise specified. Data from unscheduled visits will not be summarized but will be presented in the data listings.

All analyses and outputs will be generated using SAS® version 9.4 (or higher).

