5. Other therapies for NAFLD or NASH: requires a stable regimen for at least 3 months prior to the Screening biopsy of record and throughout the study. May include vitamin E, milk thistle, thiazolidinediones and pentoxifylline.

Double-Blind Cohort:

Includes statins.

Open-Label Single Blind and Placebo Controlled 24 Week Histology Cohorts:

Includes statins if the conditions below are met. Other therapies may include vitamin E ( $> 800$  IU Placebo cohort only), milk thistle, thiazolidinediones (open-label, single-blind only) or pentoxifylline.

- a. Patient can be defined as statin naïve or experienced at Screening based on the following definitions:
  - i. **Statin-naïve:** no administration of statins within 3 months prior to enrollment.
  - ii. **Statin experienced:** administration of  $\leq 50\%$  of the maximal dose of current statin therapy.
- b. Requires a stable regimen for at least 3 months prior to Screening through Week 2.

The following are the acceptable daily doses of approved statin therapies, including combination preparations of statins and other lipid lowering agents. Also listed under Concomitant Medications in [Section 9.7](#).

- Atorvastatin:  $\leq 40$  mg/d
- Fluvastatin:  $\leq 40$  mg/d
- Lovastatin:  $\leq 40$  mg/d (immediate release),  $\leq 30$  mg/d (extended release)
- Pitavastatin:  $\leq 2$  mg/d
- Pravastatin:  $\leq 40$  mg/d
- Rosuvastatin:  $< 20$  mg/d (Note: must be  $<$  not  $\leq$  20 mg/d)
- Simvastatin:  $\leq 40$  mg/d

6. The following liver enzyme parameters must be met at Screening:
  - a. ALT and AST  $\leq 250$  IU/L
  - b. Abnormal ALT defined as:  $\geq 30$  IU in males and  $\geq 19$  IU in females
  - d. AST  $\geq 30$  IU/L except for patients with a historical biopsy within 3 months of screening with NAS of at least 4 with 1 point in each component and fibrosis stage 2 or 3 (Placebo-Controlled Cohort only)
7. The following additional laboratory parameters must also be met at Screening:

- a. Total bilirubin must be within normal range. For patients diagnosed with Gibert's Syndrome, please contact medical monitor/designee
  - b. INR  $\leq$  1.3 (in the absence of warfarin or other anticoagulant therapy)
  - c. Creatinine clearance  $\geq$  90 mL/min as calculated by Cockcroft-Gault equation
  - d. Alpha fetoprotein (AFP)  $<$  100 ng/mL
  - e. LDL C  $\leq$  185 mg/dL (except Double-blind cohort and  $\leq$  165 mg/dL for the Open-Label Single Blind )

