## **8.2 Discontinuation of Study Treatment for an Individual Subject**

Study treatment will be discontinued if any of the following CTCAE categories are observed:

- Any related Grade 3 TEAE
- Any Grade 4 or higher TEAE

Additionally, subjects will be evaluated for possible discontinuation if the following changes in liver-related laboratory parameters are observed:

- Elevation of ALT > 2x above subject-specific baseline value (calculated using the median of the Screening and Day 1 value) and total bilirubin > 2x ULN:
  - ALT, AST, and total bilirubin must be re-tested within 72 hours.
  - Subjects with persistent elevations above the defined thresholds should be evaluated for discontinuation of study drug(s), independent of whether they are symptomatic or not.
- Elevation of only ALT > 2x above subject-specific baseline:
  - ALT, AST, and total bilirubin must be re-tested within 72 hours.

- Subjects with persistent elevations above the defined thresholds who are *symptomatic* should be evaluated for discontinuation of study drug(s).
- Subjects with persistent elevations above the defined thresholds who are *asymptomatic* may continue treatment under protocol-defined close observation criteria.
- Subjects continuing treatment under *close observation* should implement study procedures and assessments as part of the study conduct:
  1. Repeat liver enzyme and serum bilirubin tests two or three times weekly. The frequency of retesting can decrease to once a week or less if abnormalities stabilize or the trial drug has been discontinued and the subject is asymptomatic.
  2. Repeat additional tests to evaluate liver synthetic function (e.g., INR, direct bilirubin) as appropriate.
  3. Obtain a detailed history of symptoms and prior or concurrent diseases.
  4. Obtain a history of concomitant drug use (including nonprescription medications and herbal and dietary supplement preparations), alcohol use, recreational drug use, environmental toxin exposure, and special diets.
  5. Rule out acute viral hepatitis and other acute or chronic hepatobiliary diseases.

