For the double-blind cohort, dose reductions will be allowed on a case by case basis for subjects receiving 6 mg or matched 6 mg placebo for safety or tolerability, but must be approved by the Medical Monitor. If approved, the subject will be decreased to 3 mg or the matched 3 mg placebo to be aligned with whether they were initially receiving active drug or placebo prior to the dose reduction. Subjects receiving 3 mg or matched 3 mg placebo will not be allowed to dose-reduce during the study period.

For the open-label single-blind cohort, no dose reductions will be allowed.

For the placebo-controlled 24-week histology cohort **no dose reductions** will be allowed. Additionally, ALT, AST, and all lipid laboratory results are blinded starting with Week 2 onward. The Medical Monitor will be reviewing and monitoring all laboratory results and if any of the liver related testing parameters are observed, investigators will be notified immediately to discuss further evaluation.

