9.3. LABORATORY EVALUATIONS

Laboratory data (hematology, biochemistry, and urinalysis) will be summarized by treatment group, fibrosis stage and time point. Actual values and change from baseline will be presented for lab parameters with continuous measures. In addition, frequency tabulations of categorical urinalysis lab parameters will also be presented by treatment

Amendment Final V 2.0

group and time point. Shift tables from baseline clinical grade (low/normal/high) will also be presented for chemistry and hematology laboratory parameters.

Individual data listings of laboratory results will be presented for each subject. Laboratory values will be compared to normal ranges; out of range and clinically significant laboratory values will be identified in the listings (low, high).

Anti-drug antibodies, neutralizing antibodies and urine microscopy evaluation will be listed only.

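### No visible by-arm table in the SAP for the 24-week cohort counts subjects who meet the protocol 8.2 liver criteria, and confirmatory and close-observation results go only to listings

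*SAP*

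**What the plan says.** - **SAP 6.1 (General Methods):** "In general, only data from nominal scheduled visits will be presented in the summary tables and figures unless otherwise specified"; and "Data from unscheduled visits will not be summarized but will be presented in the data listings". The default statistics for numeric data are n, mean, SD, median, minimum and maximum, and tables are by treatment group. SAP 6.4 applies no visit windows, so a re-test cannot enter a table through the nearest visit.
- **SAP 9.3 (Laboratory Evaluations):** actual values and changes are summarised by arm, fibrosis stage and time point. "Shift tables from baseline clinical grade (low/normal/high) will also be presented for chemistry and hematology laboratory parameters". The section does not say to which post-baseline value the shift runs, and its visible text makes no exception for unscheduled results.
- **SAP 8.2.4:** the percentage of subjects within the normal range is tabulated for AST, ALT, total and direct bilirubin and GGT, by arm and visit.
- **Protocol 8.2:** the liver criterion is ALT above twice the subject's baseline (median of Screening and Day 1), alone or with total bilirubin above 2x ULN. A re-test is due within 72 hours. Close observation for asymptomatic subjects who stay on treatment reads: "Repeat liver enzyme and serum bilirubin tests two or three times weekly". The frequency may later fall to weekly or less.
- **Protocol 8.2, this cohort:** "ALT, AST, and all lipid laboratory results are blinded starting with Week 2 onward". The Medical Monitor reviews all results and notifies investigators at once if the liver parameters are observed.
- **Protocol 8.1.1, item 6:** "Abnormal ALT defined as" at least 30 IU in men and 19 IU in women. Item 7 requires total bilirubin within the normal range.
- **Baseline:** SAP 6.2.1 uses the last valid value on or before first dose, unless otherwise specified. Footnote j to the schedule in SAP Appendix A repeats the protocol's median definition.

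**The concern.** The protocol monitors a per-subject threshold event, whereas the visible laboratory tables describe groups at scheduled visits. The results that confirm an event or show its peak come mostly between visits, and the SAP sends those to listings.

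The shift table adds little for ALT. The entry criterion selects for raised values, so many subjects may start above the laboratory's ULN, and for them any multiple of baseline stays in the high category.

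The protocol reports ALT falling on drug (sections 5.4 and 5.7), so mean changes are likely to look favourable even if a few subjects rise sharply. A reader of the tables alone could then not say how many subjects per arm met the protocol's own liver criterion, how many also met the bilirubin part, or how many were confirmed.

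**Working it through.** The documents give no figure to reproduce here. The checks set the passages against each other and use the visit schedule.

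**1. How often an elevation reaches a scheduled visit.** Scheduled on-treatment visits are at Weeks 2, 4, 6, 8, 12, 18 and 24, that is days 14, 28, 42, 56, 84, 126 and 168. The gaps are 14, 14, 14, 14, 28, 42 and 42 days. For an elevation of d days (assumed) that starts uniformly over days 0 to 168, the chance of covering a scheduled visit is the sum of min(gap, d), divided by 168.

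| d (days) | Sum of min(gap, d) | Chance |
|---|---|---|
| 3 | 7 x 3 = 21 | 13% |
| 7 | 7 x 7 = 49 | 29% |
| 14 | 7 x 14 = 98 | 58% |
| 21 | 4 x 14 + 3 x 21 = 119 | 71% |
| 28 | 4 x 14 + 3 x 28 = 140 | 83% |
| 42 | 4 x 14 + 28 + 2 x 42 = 168 | 100% |

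Short elevations can be missed. Long ones do reach the tables, though not necessarily at their peak.

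**2. Results that stay in listings.** At two to three tests a week, close observation gives 4 x 2 to 4 x 3 = 8 to 12 results between Weeks 8 and 12, and 6 x 2 to 6 x 3 = 12 to 18 between Weeks 12 and 18 or 18 and 24. One scheduled value closes each interval. These are upper ranges, because testing may be relaxed, and they count results, not missed subjects.

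**3. What the ALT shift shows.** The laboratory ULN is not given, so 30, 35, 40, 45 and 55 IU/L are assumed. Each case is a rise to just over twice baseline.

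| Baseline ALT | Just over | Shift category |
|---|---|---|
| 19 (entry floor, women) | 38 | normal to high at ULN 30 and 35; normal to normal at 40 to 55 |
| 30 (entry floor, men) | 60 | normal to high at every ULN |
| 45 | 90 | high to high at ULN 30 to 40; normal to high at 45 and 55 |
| 90 | 180 | high to high at every ULN |

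The shift hides the event for many subjects, but not all.

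**4. What mean, maximum and change show.** Suppose one of 50 subjects rises from 80 to 400 IU/L. If the 400 falls at a scheduled visit, the arm mean moves by (400 - 80)/50 = 6.4 IU/L, while the printed maximum can be no less than 400 and, with an SAP baseline of 80, the maximum change no less than 320. If the 400 is an unscheduled value, none of the three appears in a laboratory table.

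**5. The two baselines.** The median of two values is their mean.

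- Screening 60, Day 1 100: the protocol 8.2 baseline is 80 and the trigger is above 160. Twice the SAP baseline is 200. A value of 180 meets the protocol criterion but is only 1.8 times the SAP baseline.
- Screening 100, Day 1 60: the trigger is again above 160, but twice the SAP baseline is 120. A value of 140 is 140/60 = 2.3 times the SAP baseline and does not meet the protocol criterion.

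Change from the SAP baseline therefore cannot stand in for the protocol criterion.

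**The case against.** A reader might infer that the liver-injury pattern cannot appear in any by-arm table. The documents do not support that:

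- Maxima of ALT, AST and bilirubin, and of their changes, are printed by arm at each scheduled visit.
- Total bilirubin must be normal at entry (Gilbert's syndrome is referred to the medical monitor), so a scheduled value above 2x ULN is normally a visible normal-to-high shift. SAP 8.2.4 adds percent-normal tables.
- Sites do not see ALT or AST from Week 2, but the Medical Monitor must tell them when the liver parameters are observed. Clinically relevant laboratory changes are adverse events (protocol 11.1), and the SAP 9.2 tables by term, grade, seriousness and withdrawal are not tied to visits.
- The first triggering value will often come from a scheduled visit.
- The rule in SAP 6.1 is a general one that allows exceptions.
- Protocol 12.10.2 promises only descriptive summaries and optional shift tables for routine laboratory values, and the SAP provides these. The 8.2 thresholds guide individual management and are not an endpoint.
- Listings are sorted by arm and flag out-of-range and clinically significant values, which is manageable for about 75 subjects.
- The table index and part of SAP 8.2.4 are redacted, and the mock-ups are a separate document, so a dedicated liver table may exist.

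All of this stands, and it rules out the strong reading. What it leaves is that each route shows a component. None visibly counts subjects who met the criterion, links ALT to bilirubin in the same subject, or shows confirmation. The adverse event route also depends on notification and on the investigator's judgement, since nothing visible requires an entry when a threshold is met.

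**Conclusion.** The point holds in a narrow form: a worthwhile, low-cost improvement to safety reporting in this cohort, not a flaw that invalidates the plan. The main gap is the missing per-subject threshold count. The scheduled-visit rule and the low/normal/high categories make it worse, and summarising unscheduled values alone would not close it.

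On size, elevations of 7 to 14 days would cover a scheduled on-treatment visit 29% to 58% of the time, and those of 42 days always. This rests on assumed durations and a uniform start. A just-triggering rise from 90 IU/L is invisible in the shift table at every assumed ULN from 30 to 55, while one from 30 IU/L is visible at all of them. No number of missed subjects can be given, because neither the event rate nor the laboratory ULN is in the documents. The conclusion concerns visible text only, and the other cohorts have separate analysis plans.

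**What to change.** 1. Check the redacted table index and the mock-ups. If a liver table by arm already exists, confirm that it uses all post-dose results and the protocol 8.2 baseline; step 4 is then met.
2. In SAP 6.1 and 9.3, keep by-visit summaries on scheduled data, and state that worst post-baseline liver values use all post-dose results: scheduled, repeat and unscheduled.
3. Replace or supplement the ALT and AST shift with a baseline-to-worst shift in multiples of ULN and of baseline.
4. Add one table by arm with the number of subjects whose worst ALT exceeded twice the protocol 8.2 baseline, with and without total bilirubin above 2x ULN, and the number confirmed on re-test.
5. State in SAP 6.2.1 that this table uses the median of Screening and Day 1, so that it agrees with protocol 8.2 and footnote j.

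The cost is SAP wording and one or two extra safety tables from data already collected. Nothing changes for sites or for the clinical rules.
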